## PRÉCIS

### Overview and Objectives

Polypharmacy is prevalent among older adults and associated with numerous adverse outcomes. Persons with Dementia (PWD) experience even higher levels of polypharmacy compared to those without dementia. PWD are also at greater risk for potential harm from polypharmacy including adverse drug reactions, falls, and further cognitive decline. Furthermore, deprescribing decisions among PWD (and their respective caregivers) have unique factors that must be considered. First, PWD are likely to require the input of a caregiver or healthcare proxy to make deprescribing decisions. Importantly, there are measurable differences between PWD and their proxies related to their attitudes toward deprescribing, with reduced willingness to deprescribe among proxies in the population-based sample completing the National Health and Aging Trends Study (NHATS). Despite the prevalence and associated risks of polypharmacy among PWD, few interventions have targeted deprescribing among the high-risk population of PWD. Importantly, deprescribing interventions, to date, among PWD largely have been implemented within outpatient clinical settings or otherwise excluded those receiving dementia care in assisted-living facilities (ALFs). PWD, especially those with advanced disease, may commonly live in ALFs. There currently exists a substantial gap in our understanding of deprescribing among ALF residents with advanced dementia. There are a number of important considerations within an ALF dementia care facility intervention. First, family proxies play a primary role in deprescribing decisions for PWD who reside in these care settings. In addition to family proxies' unique attitudes and behaviors, one must also consider the attitudes and behaviors of the licensed caregivers (nursing and physician staff) responsible for daily care. Although unique barriers to deprescribing may exist, there also may be potential advantages of an ALF-based deprescribing intervention, most notably the ability to more frequently monitor for potential withdrawal symptoms or other impacts of deprescribing, which may address family and/or licensed caregiver concerns about the effects of deprescribing on quality of life.

Our research team recently completed a patient-centered deprescribing intervention (Shed-MEDS) that targeted older hospitalized adults that required ongoing post-acute care (PAC). The nurse-practitioner or pharmacist-led deprescribing intervention resulted in statistically significant reductions in total medications and the combined burden of anticholinergic and sedative medications as measured by the drug burden index. Reductions were achieved at the end of the intervention (at the time of PAC discharge), and up to 90 days following the end of the intervention. Despite these successes, we do not know the feasibility or effect-size of a similar intervention implemented in a memory care ALF for PWD and their proxies. Thus, we aim to perform a single-arm, repeated-measures within-subjects feasibility pilot of the Shed-MEDS deprescribing intervention among PWD experiencing polypharmacy and their caregivers at the Abe's Garden dementia care ALF. **Our overarching hypothesis is that implementing the Shed-MEDS deprescribing protocol within a dementia care ALF will be feasible and reduce medications without worsening the quality of life for PWD.**

**Specific Aim 1:** Determine the feasibility of implementing the Shed-MEDS deprescribing intervention among PWD residing in a dementia care ALF.

- Aim 1a. Family proxy acceptability will be measured via the revised Patient Attitudes Toward Deprescribing (rPATD) designed for surrogates and through documentation of barriers and enablers to deprescribing recommendations shared via proxy interviews.
- Aim 1b. Implementation of the Shed-MEDS intervention will be assessed by the proportion of deprescribing recommendations acceptable to primary prescribers and family proxies of PWD.

**Specific Aim 2:** Document the effects of the Shed-MEDS deprescribing intervention on medication burden among PWD.

- Aim 2a: Compared to a pre-intervention period, the Shed-Meds intervention will result in significant increases in the total number of medications deprescribed, as defined by terminations at the end of 90 days.

- Aim2b: Compared to a pre-intervention period, the Shed-Meds intervention will result in a significant decrease in the anticholinergic and sedative drug burden of prescribed medications at the end of 90 days.

**Specific Aim 3:** Document the effects of the patient-centered deprescribing intervention (Shed-MEDS) on the quality of life of PWD.

- Aim 3a: The Shed-MEDS intervention will not result in significant reductions in quality of life, as measured by Behavioral and Psychological Symptoms of Dementia (BPSD) events and DEMQOL-proxy scores at the end of 90 days.

**Potential for Impact:** The data from this study will inform feasibility and the implementation barriers and facilitators specific to PWD, their family proxies, and dementia care ALF staff. This information will inform tailored adaptations to the Shed-MEDS intervention in preparation for a multi-center R01 trial to test the clinical effectiveness of deprescribing among PWD in ALF care settings.

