## Study Design and Outcomes Overview

This is a single arm pilot and feasibility study to adapt the Shed-MEDS intervention to the memory care setting. The Shed-MEDS intervention is a multistep deprescribing protocol which considers patient and disease factors, life expectancy, goals of care, and appropriate treatment targets. Medication-specific factors such as drug-drug interactions, drug-disease interactions, and drug-specific safety profiles are also incorporated. Finally, patient preferences and primary prescriber input are key to final deprescribing actions by identifying the medications patients are willing to deprescribe and seeking their primary prescriber's agreement. In this intervention, deprescribing is defined as either stopping a medication or reducing the dose/frequency of a medication.

The primary study setting is two assisted living facilities (ALFs) with dedicated memory care units.

Eligible residents are ALF residents aged 65 years or older with a dementia diagnosis and experiencing polypharmacy as defined by 5 or more medications.

Primary Outcome is the number of medications deprescribed, either stopped or reduced dose, 90-days after intervention completion.

Secondary Outcome is the impact of deprescribing on behavioral symptoms of dementia and resident quality of life.

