## Interventions and Duration

The Shed-MEDS Intervention (Figure 1. Stage 2) includes identification of medications for deprescribing, a surrogate preference interview, and discussion with residents' primary care providers (ALF and outside providers). The intervention ends after the final agreed upon deprescribing actions were communicated to the ALF providers. Follow-up data collection and assessments were conducted at 30-, 60-, and 90-days after completing intervention.

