### Schedule of Assessments

**Table 1. Data Collection Schedule**

Measures	3-month Retrospective Review ∞	Enrollment	30- & 60-day Follow-up	90-day Follow-up
Demographics and Health Status				
Age, Gender, Race/Ethnicity, Education Level*		X		
Comorbidities*		X		
Cognitive Impairment (BIMS)	X*	X		X
Status: Long-Term Care, Hospice, Death*	X	X		X
Medications				
Total number of medications*	X	X	X	X
Sedative & Anticholinergic Drug Burden Index	X	X	X	X
Quality of Life				
DEMQoL-Proxy		X		X
BPSD*	X	X	X	X
Safety				
Falls*	X	X	X	X
Emergency Room Visits & Hospitalizations*	X	X	X	X
Feasibility				
RPATD (surrogate)		X		
Surrogate agreement w/ deprescribing recommendations		X	X	
Provider agreement w/ deprescribing recommendations		X	X	
Total number of conversations w/ prescribing MD/NPs		X	X	X
Total number of conversations with surrogates		X	X	X

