Revised Patients' Attitudes Toward Deprescribing (rPATD) is a 19-item survey with 5-point Likert scale ranging from 'strongly agree' to 'strongly disagree.' Examples include: "I feel that I am taking a large number of medicines" and "I believe that all my medications are necessary." There is not an overall, global score for the assessment. Instead, a score ranging from 1-5 is assigned for each of the five factors: Burden, Appropriateness, Concerns about stopping, and Involvement. Higher scores in the burden, concerns about stopping, and involvement in treatment domains indicate a greater burden, concern, involvement. Questions regarding the appropriateness factor are scored in reverse. Thus, higher scores in the appropriateness domain indicate a participant's/surrogate's belief in the appropriateness of their medications. This tool was validated for use with surrogates.

Surrogate agreement with study deprescribing recommendations: The total number of medications the surrogate agrees to deprescribe will be totaled. For analysis purposes, medications will also be organized into medication classes.

Provider agreement with study deprescribing recommendations: The total number of medications the medical provider (i.e. Abe's Garden MD/NP or outside provider) agrees to deprescribe will be totaled. For analysis purposes, medications will also be organized into medication classes.

Total number of conversations with surrogates: We will record the total number of conversations with surrogates about the resident and the deprescribing process.

[figure not shown]
Total number of conversations with prescriber: The total number of conversations with the prescribing MD/NP as they are related to the deprescribing process will be recorded.

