### Pre-Review (Target Medications for Deprescribing)

Using medical record data only, a study NP will gather the following information for each medication: (1) Medication – Indication pairing: For each medication, an indication (i.e., diagnosis or symptom) will be identified. If an indication does not exist, “no indication indicated” will be specified; and, (2) De-prescribing rationale: Each medication will be assessed for the potential rationales for deprescribing shown in Table 2, indicating all applicable rationales.

All medications, both prescription and OTC including vitamins and herbal supplements, are reviewed for potential deprescribing. Select medication classes will not be under consideration for active deprescribing, which include the following:

- Anti-rejection medications for organ/ bone-marrow transplantation
- Chemotherapeutic medications for the treatment of known solid organ or hematologic malignancy.

The above medications may be deprescribed during the study period; however, it would solely be under the direction of the primary prescriber of the medication.

Deprescribing Priority: Although any rationale may be appropriate for deprescribing medications, a study NP will establish a priority level of 1 (low) to 10 (high) for discussing deprescribing recommendations. Priority will consider potential harm of the medication and potential effects on geriatric syndromes. It may be inappropriate to deprescribe multiple medications simultaneously; thus, prioritization may guide the surrogate interview and the deprescribing order.

**Deprescribing Action Recommendations:** For any medications recommended for deprescribing, the study NP will recommend a deprescribing action: (1) Stop now without need for monitoring; (2) Stop with symptoms/physiologic monitoring; (3) Stop at specified time point; (4) Reduce over time with monitoring until medication is stopped; (5) Reduce to lower dose without need for monitoring; (6) Reduce to lower dose with symptoms /physiologic monitoring. All recommendations will be discussed with primary prescribers (**Step 2b**) and surrogate decision-makers (**2c**).

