### Final Deprescribing Actions

The final step in the intervention is to review the final list of medications all parties (surrogate and provider) agreed to deprescribe with the ALF NP/MD and have them update the medication orders in the ALF EMR.

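### Aim 1b measures agreement with recommendations and calls it implementation; no prespecified measure follows each recommended change to an order or to its day-90 status

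*Combined protocol and SAP*

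**What the plan says.** Overview and Objectives sets Aim 1b: "Implementation of the Shed-MEDS intervention will be assessed by the proportion of deprescribing recommendations acceptable to primary prescribers and family proxies of PWD". Proxy acceptability already has its own sub-aim, 1a, measured by the rPATD and by recorded barriers and enablers.

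The study team does not write orders. Under Final Deprescribing Actions it takes the agreed list to the facility NP or physician to "have them update the medication orders in the ALF EMR". Interventions and Duration fixes the end point of the intervention: "The intervention ends after the final agreed upon deprescribing actions were communicated to the ALF providers". Follow-up at 30, 60 and 90 days runs from there.

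The Feasibility block of Table 1 holds the rPATD, surrogate agreement, "Provider agreement w/ deprescribing recommendations", and counts of conversations with surrogates and prescribers. The two agreement rows are scheduled at enrollment and at 30 and 60 days. The Secondary Outcomes section defines the surrogate variable as a count: "The total number of medications the surrogate agrees to deprescribe will be totaled". The provider variable is defined the same way.

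Medication use is measured separately. Table 1 schedules total medications and the Drug Burden Index (DBI) at the retrospective review, enrollment, 30, 60 and 90 days, with the MAR as the main source for the medication count. Study Design and Outcomes Overview states: "Primary Outcome is the number of medications deprescribed, either stopped or reduced dose, 90-days after intervention completion". Aim 2a describes that count more narrowly, predicting "significant increases in the total number of medications deprescribed, as defined by terminations at the end of 90 days". Under Statistical Considerations, Outcomes, each resident's 3-month retrospective review is the control.

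**The concern.** Between agreement and an actual change in treatment lie steps the study team does not control: the order must be entered, any taper or delayed stop completed, and the drug not restarted. The Pre-Review section makes the interval real, since its action list includes stops at a later time point and gradual reductions, and it allows that several drugs may not be suitable for change at once. Some agreed changes can therefore take effect only after the intervention has formally ended. A measure that stops at agreement does not measure what Aim 1b names.

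The primary count comes from the other end of the chain and is not tied to the recommended list. It can include changes made outside the study process. For the two drug classes that the study does not target, Pre-Review says so directly: "The above medications may be deprescribed during the study period; however, it would solely be under the direction of the primary prescriber".

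The pilot is meant to guide adaptations before a multi-center trial. If the medication effect is small, three explanations call for different adaptations: the change was refused, it was agreed but never ordered, or it was ordered and later reversed. Barrier and enabler coding explains the first. No prespecified measure separates the other two.

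**Working it through.** **1. What is recorded at each step, drug by drug**

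| Step | Who acts | What the plan records |
|---|---|---|
| Recommended | Study NP | Action, rationale and priority per drug |
| Agreed | Surrogate, prescriber | Agreement and reasons per drug; totals for analysis |
| Ordered | Facility NP/MD | A procedure step; no variable tied to the recommendation |
| In place at 30, 60, 90 days | Facility and outside prescribers | MAR and DBI; no link to the recommendation |

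The plan states no ordering or persistence rate, so there is no figure of its own to reproduce.

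**2. Agreement as a bound**

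Let A be the proportion of recommendations agreed, o the proportion of agreed changes ordered, and k the proportion of ordered changes still in place at day 90.

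- Enacted = A × o; gap = A × (1 − o)
- Kept to day 90 = A × o × k; gap = A × (1 − o × k)

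Both gaps are zero only if o = k = 1. For illustration, A = 64% comes from Background and Significance (surrogates in the earlier hospital-based Shed-MEDS trial), with 50% (participants deciding for themselves) as a second starting value. Both are one party's agreement, not joint agreement with prescribers. The values of o and k are assumed.

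| o = k | Enacted, A = 64% (gap) | Kept, A = 64% (gap) | Kept, A = 50% (gap) |
|---|---|---|---|
| 100% | 64.0% (0) | 64.0% (0) | 50.0% (0) |
| 90% | 57.6% (6.4) | 51.8% (12.2) | 40.5% (9.5) |
| 80% | 51.2% (12.8) | 41.0% (23.0) | 32.0% (18.0) |
| 70% | 44.8% (19.2) | 31.4% (32.6) | 24.5% (25.5) |

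The two gaps should be kept apart. The enactment gap bears directly on the word implementation. The day-90 gap adds persistence, which Aim 1b does not claim to measure.

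A itself is not fully defined. Aim 1b is a proportion, but the agreement variables are totals. Pre-Review has all recommendations discussed with primary prescribers, whereas Outpatient & ALF Provider Input has the primary prescriber contacted, after the surrogate interview, about the agreed medications. The provider denominator could be either set.

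**3. The 90-day count**

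Let R be recommendations per resident, D the proportion delivered and kept, and b the unrelated changes per resident over follow-up. The unrelated share of the raw count is b / (b + R × D). Assume R = 3 and D = 51.8%, so R × D = 1.555:

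- b = 0: 0%
- b = 0.25: 0.25 / 1.805 = 14%
- b = 0.5: 0.5 / 2.055 = 24%
- b = 1.0: 1.0 / 2.555 = 39%

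The share does not depend on the number of residents. With the retrospective control, whose background rate is b₀, the expected within-subject excess is R × D + (b − b₀). Background changes cancel only if b = b₀. The limitations under Data Analyses concede that time effects cannot be controlled.

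**The case against.** A reader might infer that nothing checks delivery. The documents do not support that. Updating the orders is a written step of the intervention, the study NP is to help get the record updated, MAR and DBI data are scheduled three times after the intervention, conversations are counted to day 90, and weekly follow-up is described for withdrawal events. The per-drug link is missing, not the underlying data.

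A reader might also infer that the pilot could not tell failed delivery from success. In aggregate it could: high agreement with few changes would appear as a high Aim 1b figure beside a low primary outcome. What would stay hidden is where the chain broke, or whether a large count consisted mostly of drugs that were not recommended.

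The retrospective comparison is a real answer to the mixing of study-driven and other changes, and the plan discloses its weakness. Nor do the documents show that unrelated changes are common. The untargeted classes are only anti-rejection drugs and chemotherapy. The 12 hospice beneficiaries among 41 residents describe one facility at inception, not hospice transitions or medication changes during follow-up.

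Finally, Aim 1b states its definition openly, and Aim 2 measures medication effect separately. That limits the harm, but the label still does not match the measure, and the recommendation-level result is still not prespecified.

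**Conclusion.** The point holds in a limited form. Aim 1b reports agreement under the name of implementation, and agreement is only an upper bound on delivery of agreed changes. It can overstate delivery, but that it does so is not shown, and the documents give nothing from which to estimate the amount. The gaps of 6 to 19 points for enactment and 12 to 33 points for day-90 status hold only for 64% agreement and assumed ordering and persistence of 70–90% each; both gaps are zero if every agreed change is ordered and kept.

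The 90-day count has no attribution rule. Its comparison with the retrospective period is sound against background changes only if their rate is stable. The 0 to 39% unrelated share is likewise an assumed range, and it applies to the raw count, not to the within-subject contrast.

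This should be changed: the pilot's purpose is to inform delivery in a larger trial, and the needed data are largely in hand. It does not invalidate the primary outcome.

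**What to change.** Keep agreement, under the name acceptability. Redefine Aim 1b implementation from the MARs already collected: for each recommended change, record whether it was agreed, ordered as agreed, and in place at 30, 60 and 90 days. Report, each over the number of changes recommended, the proportions (a) agreed, (b) enacted and (c) still in place at day 90, with reversals (drug restarted or dose restored) listed.

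State the denominators, including whether provider agreement is taken over all recommendations or only those the surrogate accepted. Give separate codes to changes not yet due and to residents without day-90 data: at the planned 10–15% attrition of 40, that is 4 to 6 residents. Over-the-counter products that families supply directly may not appear in the MAR, so ask about them at the 90-day interview or code them as not observable.

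As a supplementary table, split the 90-day primary count into changes on the study's recommended list and all others. Reconcile Aim 2a, which counts terminations, with the primary outcome, which also counts dose reductions, so that the table has one definition. If results have already been seen, date the change and say so in the report.

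The cost is a few hours of abstraction, a wording change to Aim 1b, and probably a lower headline implementation figure.

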## Study Population and Sample Size

The eligible patient population are ALF residents with a dementia diagnosis, age  $\geq 65$  with polypharmacy as defined by  $\geq 5$  medications (or the presence of at least 1 PIM). The expected enrollment is 40 PWD with an estimated attrition rate of 10-15%.

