## STATISTICAL CONSIDERATIONS

### Sample Size & Attrition

Abe's Garden administration reported that all current residents lack decision-making capacity for healthcare decisions, and that all have surrogate decision makers. We estimate that the majority of the 41 residents/surrogates will participate in the study and conservatively estimate, based on investigators' work in previous studies in long term care, that attrition will be approximately 10-15%. We anticipate that some residents may die during the study and some surrogates may decline participation.

Power consideration: Given this is a pilot study, no formal power analysis will be conducted. But this pilot data would serve as a further guide for the power analysis for the following multi-center trial in preparation to test the clinical effectiveness of deprescribing among PWD in ALF care settings.

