### Outcomes

Aim 1: Descriptive statistics (counts and proportions for categorical variables and means and SDs for continuous ones) will be used to describe Demographics at baseline, as well as Feasibility outcomes in Aim 1 at each measurement.

Aims 2 and 3: All statistical tests will be two-sided, with alpha = 0.05. For Aims 2 and 3, we will be applying a within-subjects intervention design to estimate the effect size of Shed-MEDS deprescribing intervention on Medication and Quality of Life outcomes. This design takes advantage of the smaller sample size in this pilot intervention, with each subject's 3-month retrospective review serving as their own control, which also removes the between-subjects differences in each condition. For the Medications outcomes in Aim 2 and the Quality of Life outcome of BPSD in Aim 3a, changes during the intervention period will be modeled using GEE, where time (multiple indicators), intervention group (one indicator) and their interaction will form the predictors, controlling

for baseline demographics. Hypothesized differences between the intervention and control groups will be examined using appropriate linear contrasts. For the DEMQoL-Proxy in Aim 3a, we will use a two-sample t-test to compare measurements at baseline with the 90-day follow-up, which is robust against normality or heterogeneity of variance.

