## Data Analyses

Missing Data: We will examine the incidence of missing data for each outcome in Table 2. We acknowledge that although the missing data could be informative due to intervention-related death or surrogate decision, we will not have enough data to formally test it due to the extremely small number of anticipated attrition (<5).

Repeated measures: Barring study withdrawal or death, main outcomes including the total number of medications, Quality of Life, and Safety will be assessed at four time points (enrollment, 30, 60, and 90 days) for each participant. We account for the anticipated positive correlations using a generalized estimating equation (GEE) framework for each repeated outcome. Unlike the parametric generalized mixed-effects models, GEE imposes no mathematical model for data distribution, thus providing valid inference for a broader class of data distributions.

Limitations: There are a number of limitations that must be acknowledged in this pilot deprescribing study. The most apparent is the limited sample size. Although small, the sample size is sufficient to understand the primary feasibility aims of our study, applying Shed-MEDS in this novel population of PWD in an ALF. We have selected a within-subjects study design to maximize the power to estimate effect sizes on medication and quality of life outcomes for subsequent larger randomized trials. Without a concurrent, randomized comparator, there is a potential for time-related threats to validity, as we cannot control the effects of time on the outcomes. Furthermore, we would not be able to rule out carryover effects of earlier treatments on the outcomes.

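### As worded, Aim 3a is met by a non-significant result, which cannot show that quality of life is preserved, and the planned unpaired t-test makes that result more likely

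*Combined protocol and SAP*

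**What the plan says.** The overarching hypothesis in the Précis (Overview and Objectives) is that the intervention "will be feasible and reduce medications without worsening the quality of life for PWD". Aim 3a turns the quality-of-life part into a prediction that "The Shed-MEDS intervention will not result in significant reductions in quality of life", judged at 90 days on BPSD events and DEMQOL-Proxy.

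Under Statistical Considerations, Outcomes, the rule for Aims 2 and 3 is: "All statistical tests will be two-sided, with alpha = 0.05". BPSD is modelled by GEE. For the other measure: "For the DEMQoL-Proxy in Aim 3a, we will use a two-sample t-test to compare measurements at baseline with the 90-day follow-up". The same section describes a within-subjects design whose purpose is to estimate effect sizes.

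On size, Study Population and Sample Size says: "The expected enrollment is 40 PWD with an estimated attrition rate of 10-15" per cent. Sample Size & Attrition says: "Given this is a pilot study, no formal power analysis will be conducted". No section gives a margin, an equivalence bound, a confidence-interval rule or a smallest important change for either measure.

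**The concern.** A difference test asks whether the data contradict no change. Failing to contradict it is not evidence that change is absent or small. When the hoped-for outcome is a lack of significance, a smaller or noisier study reaches it more easily, and so does a less efficient test.

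The choice of test adds to this. Baseline and 90-day DEMQOL-Proxy scores come from the same residents. A two-sample t-test treats them as two independent groups, so with positively correlated scores it overstates the standard error of the change.

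What is at stake is whether the pilot may report that medications were reduced without loss of quality of life. The Background notes caregiver resistance to stopping antipsychotics because of concern about behavioural symptoms, so proxies and prescribers may rely on such a statement.

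**Working it through.** The plan has no power figure to reproduce, so the check asks how often a real decline in DEMQOL-Proxy would go undetected.

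**Inputs from the documents**
- Enrolment 40, attrition 10–15%: 40 × 0.90 = 36 and 40 × 0.85 = 34 completers. The Missing Data paragraph expects an "extremely small number of anticipated attrition (<5"), which fits 10% of 40 (4 residents) but not 15% (6). Both ends are carried.
- Two-sided alpha 0.05. DEMQOL-Proxy is measured at enrolment and at 90 days.

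**Assumptions, not in the documents**
- Declines of 0.3 and 0.5 SD, equal SDs at both times, normal scores.
- Baseline to 90-day correlation r = 0.3, 0.5 or 0.7.

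**Step 1: what ignoring the pairing does.** The two-sample formula takes the standard error of the mean change as SD × √(2/n). With paired scores it is SD × √(2(1−r)/n). The true standard error is therefore √(1−r) times the one used: 0.84, 0.71 and 0.55 for r = 0.3, 0.5 and 0.7. Simulation of the planned test with no true change gives a two-sided type I error of about 2%, 0.6–0.7% and 0.1%, against the nominal 5%.

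**Step 2: how often a true decline is missed** (no significant decline found). Planned test: simulation on correlated scores, 50,000 runs per setting for n = 34 and 200,000 for n = 36. Paired test: noncentral t with n−1 degrees of freedom and noncentrality d√n / √(2(1−r)), where d is the decline in SD.

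| n | r | 0.3 SD, planned | 0.3 SD, paired | 0.5 SD, planned | 0.5 SD, paired |
|---|---|---|---|---|---|
| 34 | 0.3 | 81.0% | 70.0% | 46.5% | 33.3% |
| 34 | 0.5 | 84.4% | 60.3% | 46.1% | 19.2% |
| 34 | 0.7 | 90.1% | 40.8% | 44.9% | 4.5% |
| 36 | 0.3 | 79.7% | 68.5% | 43.6% | 30.7% |
| 36 | 0.5 | 83.5% | 58.3% | 42.8% | 16.9% |
| 36 | 0.7 | 88.8% | 38.2% | 40.8% | 3.6% |

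The planned test has an even chance of detecting a decline of about 0.48 SD (n = 34) or 0.47 SD (n = 36).

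**Step 3: width of the interval, n = 34.** Two-sample formula: 1.997 × √(2/34) = 0.48 SD. Paired: 2.035 × √(2(1−r)/34) = 0.41, 0.35 and 0.27 SD for r = 0.3, 0.5 and 0.7.

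**Step 4: what an interval rule could deliver.** With true change zero, the chance that the lower limit of the paired 95% interval lies above −m is the one-sided 0.025 power for a shift of m. For n = 34 and r = 0.5, the noncentrality for m = 0.5 SD is 0.5 × √34 = 2.92 and the power is about 81%. For m = 0.3 SD it is 0.3 × √34 = 1.75 and the power is about 40%. Over r = 0.3 to 0.7 the ranges are 67–96% and 30–59%.

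The BPSD analysis cannot be checked in this way, because the documents give no event rate or dispersion.

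**The case against.** The strongest reply is that this is a declared pilot. Quality of life is a secondary outcome, the plan says that no power analysis is made, and the Limitations paragraph concedes the small sample. Aim 3 is headed as documenting effects, and both the Outcomes section and the Limitations paragraph give effect-size estimation as the purpose. This stands, and it lowers the severity. It does not remove the problem, because the wording of Aim 3a conflicts with that purpose and nothing else in the plan says how the aim would be judged. The sample is called sufficient for the feasibility aims, not for showing that quality of life is maintained.

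A reader might also infer several stronger things that the documents do not support:
- That the plan declares p > 0.05 to be proof of no harm. No section says so. The point is that the wording of the aim offers no other criterion.
- That the pilot would usually miss a moderate decline. At 0.5 SD the planned test misses somewhat under half the time and a paired test misses 4–33%. Usually is right for the planned test only below about 0.48 SD.
- That a finding of no worsening would be reached in most cases even if quality of life fell. Aim 3a covers BPSD as well as DEMQOL-Proxy, and a significant worsening on either would contradict it. With BPSD power unknown, the overall probability is unknown.
- That this result is the main message meant to justify the next trial. The Précis says the data will inform feasibility, barriers and adaptations, and Sample Size & Attrition says they will guide its power analysis. Neither makes the next trial depend on Aim 3a.

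Part of the planned test's high miss rate comes from ignoring the pairing, which is a separate fault. The paired columns show what remains after that is corrected.

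**Conclusion.** The point holds in this form: Aim 3a, followed as written, is met by non-significance, and the plan has no margin or interval rule that would let it support a statement that quality of life is preserved. The unpaired test tilts the result further in that direction. For DEMQOL-Proxy with 34 to 36 completers and assumed r of 0.3 to 0.7, a 0.3 SD decline is missed about 80–90% of the time with the planned test and 38–70% with a paired one. For a 0.5 SD decline the figures are about 41–47% and 4–33%. Even the lower planned-test figures are too high for non-significance to count as reassurance.

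The effect sizes, correlations and normality are assumptions. The number of completers is the only input to these rates, apart from alpha, that comes from the plan. This should be fixed, but since it concerns a secondary aim of an acknowledged pilot it does not undermine the feasibility aims.

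**What to change.** 1. Restate Aim 3a as estimation, in line with the purpose already given for Aims 2 and 3, and drop the absence of significance as its criterion.
2. Replace the two-sample t-test by the paired within-resident mean change in DEMQOL-Proxy with a 95% confidence interval.
3. Report the BPSD effect from the GEE with a 95% confidence interval.
4. Fix and justify a margin for each measure before analysis. Claim no worsening only if the interval excludes that margin; otherwise report the result as inconclusive.

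The cost is wording in Aim 3a and the Outcomes section, plus the work of justifying the margins. No further residents or assessments are needed. The downside is that the pilot may have to report an inconclusive result, and how likely that is depends on the margin. With true change zero, r = 0.5 and 34 completers, the chance of excluding the margin is about 81% for an assumed 0.5 SD margin but about 40% for 0.3 SD. The interval would still describe change over time in a single arm, as the Limitations paragraph already acknowledges.
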